8.1.2.3. Change from Baseline in Body Weight at Week 26 and over Time

Change from Baseline in body weight will be analyzed and summarized analogous to the primary efficacy endpoint using a slightly different MMRM model which includes change from Baseline in body weight as dependent variable; treatment, region, baseline HbA_{1c} category, age category, current metformin use, visit week, treatment-by-week interaction, and baseline weight-by-week interaction as fixed effects; baseline weight as a continuous covariate; and subject as a random effect (Model 2). Treatment difference at Week 26 will be tested; p-value and 2-sided 95% confidence interval will be presented. The percentage change from baseline in body weight will be analysed using a similar MMRM model:

Change from Baseline in Body Weight = Baseline Body Weight + Treatment + Baseline HbA_{1c} Category + Region + Age Category + Current Use of Metformin + Visit Week + Treatment-by-Visit Interaction + Baseline Body Weight-by-Visit Week Interaction (Model 2).

The percentage change from Baseline in body weight will be analyzed similarly using Model 2 above, with percent change from baseline in body weight as the dependent variable.

The observed body weight values and change and percent change from baseline body weight will be summarized descriptively and presented graphically. The least squares means (and standard errors) of change from baseline body weight will be plotted by treatment group.

The analyses will be performed on FA population and all data will be listed.

8.1.2.4. Prescribed Total Daily Insulin Doses and Total Number of Weekly Insulin Injections

Prescribed total daily insulin doses at Baseline, Week 4, 5, 10, 18 and 26 will be assessed from several aspects:

- Total daily insulin dose (IU)
- Body weight adjusted total daily insulin dose (IU/kg)
- Total daily basal insulin (insulin glargine) dose (IU)
- Body weight adjusted total daily basal insulin (insulin glargine) dose
- Total daily bolus insulin (insulin lispro) dose (IU)
- Body weight adjusted total daily bolus insulin (insulin lispro) dose

The absolute value in each of the above variables by visit will be analyzed using an MMRM model similar to Model 2 where the specific insulin dose replaces weight (Section 8.1.2.3). The prescribed total daily insulin doses will be summarized descriptively and presented graphically by treatment group. The least squares means (and standard errors) of the prescribed total daily insulin doses will be plotted by treatment group.

In addition, total number of weekly insulin injections (7 days) to achieve glycemic control at Baseline, Week 4, 5, 10, 18 and 26 will also be assessed and summarized using descriptive statistics; the value for this analysis is derived based on the number of prescribed insulin injections as follows:

- Albiglutide: 1 injection per week
- Insulin Glargine: 1 injection per day (7 injections per week)
- Insulin Lispro: 3 injections per day (21 injections per week)

For subjects who was randomized to the albiglutide arm and required re-introduction of insulin lispro, the number of injections for insulin lispro should be based on data collected in the Surveillance eCRF page. These subjects could have once-daily, twice-daily or three times daily insulin lispro injections.

Definitions for insulin dose and number of injections at Week 26 for albiglutide arm:

- Both glargine and lispro dose at Week 26 will be defined operationally as the prescribed dose at Week 25.
- For lispro number of injections at Week 26 will be defined operationally as the prescribed number of injections at Week 25. For glargine number of injections at Week 26 will be considered 1 per day.

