5.1.2. Dosing Guidance During the Treatment Period

The dosing guidance for albiglutide, insulin lispro, insulin glargine, and metformin from Baseline/Randomization through the end of the Treatment Period is summarized in **Table 2**.

Table 2 Dosing Guidance for Albiglutide, Insulin Lispro, Insulin Glargine, and Metformin Treatment

Medication	Albiglutide + Insulin Glargine Group	Insulin Glargine + Insulin Lispro Group
Albiglutide	Baseline/Randomization: Start weekly SC injection at 30 mg. Week 4: Uptitrate to 50 mg weekly SC injection for the remainder of the Treatment Period.	None
Insulin lispro	Baseline/Randomization: Each insulin lispro dose will be downtitrated to half that used in the Standardization Period. ¹ Week 4: Stop insulin lispro for the remainder of the Treatment Period; insulin lispro may be re-introduced after Week 8 (See Section 5.1.3.5)	Baseline/Randomization: Continue at the same doses as at the end of the Standardization Period and adjust doses as per instructions in Section 5.1.3.2.
Insulin glargine	Continue at the same dose as at the end of the Standardization Period ¹ and adjust dose as per instructions in Section 5.1.3.2.	Continue at the same dose as at the end of the Standardization Period and adjust dose as per instructions in Section 5.1.3.2.

Medication	Albiglutide + Insulin Glargine Group	Insulin Glargine + Insulin Lispro Group
Metformin	Subjects will remain on their current dose for the duration of their participation in the study. ²	Subjects will remain on their current dose for the duration of their participation in the study. ²
Re-introduction of insulin lispro (if required)	After Week 8: See Section 5.1.3.5	Not applicable

SC = subcutaneous.

1. As described in Section 1.3.1, the risk of hypoglycemia is increased when albiglutide is used in combination with insulin; therefore, subjects may require a lower dose of insulin and should be monitored closely.
2. Unless a decline in kidney function results in a contraindication for metformin use. Metformin is to be stopped if the subject's estimated glomerular filtration rate, calculated according to the Modification of Diet in Renal Disease formula, decreases during the study to a level where metformin is contraindicated according to its label (as appropriate for each participating country).

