5.1.3.4. Documentation of Insulin Titration

Surveillance of insulin titration and documentation will be performed centrally. Within approximately 3 business days after a subject's study visit/telephone contact, the investigator must ensure that the following data are available for review by GSK/PPD:

[figure not shown]
- Subject's SMBG values from the last 3 available days (at least 2 of which are consecutive) in the week before the study visit/telephone contact
- Insulin doses for 3 days (at least 2 of which are consecutive) in the week before the next study visit/telephone contact
- Insulin doses recommended until the next study visit/telephone contact
- Comments on any deviation to the insulin titration algorithms must be entered into the eCRFs

The data regarding titration deviations will be reviewed by GSK/PPD. Based on this information, an inquiry as to why the investigator chose to deviate from the titration algorithm may be made, particularly when details of any SMBG readings, time, and date, or hypoglycemic symptoms used in such a decision are not provided or lack clarity. Not all deviations will lead to inquiry. When the investigator receives an inquiry, a response with the reasons for not adhering to the titration guideline should be sent to GSK/PPD within approximately 3 days. Depending on the response, additional inquiries may be sent.

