2. SUMMARY OF KEY PROTOCOL INFORMATION

2.1. Changes to the Protocol Defined Statistical Analysis Plan

Any changes from the originally planned statistical analysis specified in the protocol amendment 3 (Dated: 24-SEP-2015) are outlined as follows:

Protocol	Reporting & Analysis Plan	
Statistical Analysis Plan	Statistical Analysis Plan	Rationale for Changes

 Supportive secondary endpoint: Total daily insulin dose (24-hour total international units [IU] and total units/kg body weight) over the 3 days preceding the Baseline/Randomization and Week 4, 10, and 18 visits. 	
 Use prescribed total daily insulin dose and prescribed total daily units/kg body weight for analysis. Do not use the actual dose taken or the doses over the 3 days preceding the visits. 	
 The prescribed dose reflects the investigator's assessment of what would be required to maintain or achieve glycemic control. The 'over the 3 days preceding the Baseline/Randomization and Week 4, 10, and 18 visits' text is a carryover from earlier protocol.

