5.4. Baseline and Study Day

In general, the baseline value for each variable will be defined as the last measurement collected prior to the first dose of randomized study medication.

Study day will be defined as the number of days from the first dose of randomized study medication. The date when a subject receives the first dose of randomized study medication is defined as Day 1. For events after the first dose date, study day is calculated as the difference in days between the first dose date and the date of interest, plus 1 day. For events that occur before the first dose date, study day is calculated as the difference in days between the first dose date and the date of interest. Thus, the day before first dose date is defined as Day -1.

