11.3.4. Analysis Visit Windows

Table - Analysis Visit Windows

Scheduled Visit	Target Study Day of Visit	Slotting Intervals
Week -6	-42	Visit = " SCREENING"
Week -4	-28	Visit = " STANDARDIZATION 1"
Week -1	-7	Visit = " STANDARDIZATION 4"
Baseline (Week 0)	1	Visit = " BASELINE"
Week 4	29	2 to 32 days
Week 5	36	33 to 53 days
Week 10	71	54 to 99 days
Week 18	127	100 to 155 days
Week 26 (End of Treatment Visit)*	183	Albiglutide arm: 156 to (last dose date + 25 days) Lispro arm: 156 to last dose date
Week 30**	211	For subjects completed study Albiglutide arm: >Last dose date + 25 days Lispro arm: >Last dose date
4 Week Follow-up Visit**	Last dose date + 35 days***	For subjects didn't complete study Albiglutide arm: >Last dose date + 25 days Lispro arm: >Last dose date

* Week 26 is the end of treatment visit for those subjects completing the study per-protocol. For subjects who withdraw early from active treatment, the end of treatment visit will be assigned to an analysis visit based on the visit slotting algorithm using study day and therapy phase.

** Week 30 is the 4 week post-treatment follow-up visit for those subjects completing the study per-protocol. The 4 Week Follow-up Visit is the 4 week post-treatment follow-up visit for those subjects who withdraw early from active treatment. Both visits will be assigned based on the visit slotting algorithm using therapy phase.

*** The target study day for the 4 Week Follow-up Visit for subjects who withdraw early from active treatment is set to be 5 weeks (35 days) after last dose to correspond with the timing of the 4 week post-treatment follow-up for subjects completing the study per-protocol (where last dose is at Week 25 and the follow-up visit is at Week 30).

For parameters which were not scheduled to be collected at all visits, the all-inclusive visit intervals defined for all visits (that is, the visit window table above) will still be used to slot records. However, if a value is slotted to a visit unscheduled for a parameter, it will not be summarized (and not be included in the efficacy datasets) but will be included in data listings.

For analyses on the prescribed insulin dose, the total number of weekly insulin injections and SMBG profile, visit and visit dates recorded on the eCRF are used for analysis because a specific visit date is needed to calculate the analysis values.

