11.10. Appendix 10: Multiple Comparisons & Multiplicity

A closed testing strategy will be implemented for the multiple inferential tests among the primary and key secondary endpoints to preserve overall family-wise Type I error rate of 0.05. The strategy involves pre-specification of test order [Koch, 1996].

The first test to be conducted is the primary efficacy analysis of HbA_{1c} change from Baseline at Week 26 on treatment comparison of albiglutide versus insulin lispro using non-inferiority testing. The comparison will be evaluated inferentially at the 1-sided 0.025 criterion significance level. If the non-inferiority of albiglutide is established, testing of superiority for the key secondary endpoints and the primary endpoint will proceed sequentially in a step-down manner at a 2-sided significance level of 0.05 in the following order:

- 1) Change from Baseline in body weight at Week 26
- 2) Prescribed total daily insulin dose at Week 26
- 3) Change from baseline in HbA_{1c} at Week 26

If a test for higher order endpoints above does not reach statistical significance, the results of statistical tests for lower order endpoints will not be interpreted.

Note that for one of the key secondary endpoints listed in the protocol, proportion of subjects treated with once-weekly albiglutide that are able to discontinue insulin lispro at Week 4 and do not meet prespecified criteria for severe, persistent hyperglycemia through Week 26, treatment comparison is not applicable as it is only defined for the Albiglutide + Insulin Glargine arm.

This is a treat-to-target study with the primary efficacy endpoint HbA_{1c} as the measurement. By the study design of treat-to-target, change from baseline in HbA_{1c} values in both treatment groups (Albiglutide + Insulin Glargine versus Insulin Lispro + Insulin Glargine), is expected to reach the target, and thus not expected to show a significant difference. Thus, testing of superiority for change from Baseline in HbA_{1c} at Week 26 is considered lowest priority in the hierarchy of the multiple testing procedure.

Testing on other efficacy or exploratory endpoints, if applicable, will be considered exploratory and no multiplicity adjustment will be applied. Any secondary and exploratory endpoints that do not qualify for formal statistical testing will be analyzed and have results presented with confidence intervals and nominal p-values, if applicable.

The order of the testing strategy is shown in the diagram below.

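### The SAP does not say which prescription at the randomisation visit is the Baseline insulin dose; its own rules point to the one with lispro already halved in the albiglutide arm, which would bias a confirmatory endpoint against albiglutide.

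*SAP*

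**What the plan says.** **Endpoint.** "Prescribed total daily insulin dose at Week 26" is the second of the three superiority tests in the written list in SAP 11.10, tested at two-sided 0.05 once HbA1c non-inferiority is shown. HbA1c superiority comes after it.

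**Model.** SAP 8.1.2.4: "The absolute value in each of the above variables by visit will be analyzed using an MMRM model similar to Model 2". Model 2 (SAP 8.1.2.3) has "baseline weight as a continuous covariate" and a baseline-by-week term, with dose taking the place of weight. The example code in SAP 11.11 for weight and insulin dose contains BASE and BASE*AVISITN. Protocol 8.3.3.2 also calls for the corresponding baseline covariate.

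**Measure.** The protocol's dose assessments used the 3 days before each visit, including the Baseline/Randomization visit. SAP 2.1 replaces these with the prescribed dose: "Do not use the actual dose taken or the doses over the 3 days preceding the visits".

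**Visit.** For prescribed dose, SAP 11.3.4 states that "visit and visit dates recorded on the eCRF are used for analysis". SAP 5.4 gives the general rule that "the baseline value for each variable will be defined as the last measurement collected prior to the first dose of randomized study medication", and SAP 11.5.1 says much the same.

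**What happens at that visit.** Protocol 5.1.2, Table 2, albiglutide arm only: "Each insulin lispro dose will be downtitrated to half that used in the Standardization Period". Glargine continues at its existing dose in both arms.

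**The concern.** The protocol's 3-day dose before Visit 4 was a pre-randomisation quantity. A prescribed dose looks forward. Protocol 5.1.3.4 lists "Insulin doses recommended until the next study visit/telephone contact" separately from the doses of the preceding days, and SAP 2.1 justifies the prescribed dose as the investigator's view of what control would require.

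At Visit 4 the subject is randomised and, in one arm, lispro is halved. If the prescription written at that visit is BASE, the model adjusts for a variable that treatment assignment has already changed. Adjustment then removes part of the effect being estimated. At stake are the estimate and interval for a confirmatory endpoint, the power of that test and access to the HbA1c superiority test below it, and a Baseline table that would show an imbalance created by the regimen.

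**Working it through.** **1. Which prescription is Baseline?** The relevant texts side by side:

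- SAP 11.3.4 assigns prescribed dose to a visit by its eCRF label. SAP 2.2 lists the dose at the Baseline/Randomization visit.
- SAP 8.1.2.4 replaces the albiglutide arm's Week 26 dose with the Week 25 prescription. SAP 6.7 gives the reason in connection with lispro re-introduction: the last albiglutide injection is at Week 25, and lispro prescribed at Week 26 may be standard care. The SAP thus recognises that a visit's prescription describes the period that follows. It corrects for this at the end of treatment and has no matching rule at the start.
- SAP 5.4 and 11.5.1 require only a value before the first randomised dose. A Visit 4 prescription written before the first injection qualifies. So does the last Standardization prescription, if the Visit 4 entry is regarded as part of the randomised regimen.
- SAP 6.8 has prescriptions captured from Visit 2 (Week -4), so a pre-randomisation value exists.

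The newly written prescription is the more natural reading, but no text settles it.

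**2. The plan's own figures.** None is given for insulin dose. The HbA1c sample size, used below only for n, reproduces: 2 × (1.2/0.3)² × (1.960 + 1.282)² = 336.3, so 337 per arm; 337/0.85 = 396.5, so 397 randomised per arm.

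**3. Size of the shift.** For a linear model with fitted Week 26 baseline slope b,

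adjusted difference = (mean Y albiglutide − mean Y lispro arm) − b × (mean BASE albiglutide − mean BASE lispro arm).

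Incoming doses are equal in expectation. Halving lispro (mean L) in one arm makes the BASE difference −L/2, so the adjusted difference moves by **+b × L/2**, towards a higher albiglutide-arm dose.

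| Assumed mean lispro L (U/day) | b = 0.5 | b = 0.7 | b = 0.9 | b = 1.0 |
|---|---|---|---|---|
| 20 | 5.0 | 7.0 | 9.0 | 10.0 |
| 30 | 7.5 | 10.5 | 13.5 | 15.0 |
| 40 | 10.0 | 14.0 | 18.0 | 20.0 |
| 50 | 12.5 | 17.5 | 22.5 | 25.0 |

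At the 70-unit bolus entry limit (Protocol 4.2) with b = 1.0 the shift is 35 U. That is not a ceiling at Week 0, because lispro may be adjusted during Standardization.

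SAP 8.1.2.4 analyses the absolute dose, while the example code uses CHG. With BASE and BASE-by-week in the model, the Week 26 contrast is the same: the raw difference gains L/2 and the slope falls by 1, so the shift is L/2 + (b − 1) × L/2 = b × L/2.

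**4. Simulation check.** The setup was 337 per arm and 1,000 runs, with assumed mean glargine/lispro of 40/20, 45/35 and 50/50 U, CV 45% and residual SD 15 U. The comparator's Week 26 dose was 1.2 times its incoming total. This gives fitted slopes of 1.15 to 1.29 with the halved covariate, above the range in the table.

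| Mean lispro (U) | Week 26 doses | Incoming dose as BASE | Halved dose as BASE |
|---|---|---|---|
| 20 | equal | +0.1 | +12.4 |
| 35 | equal | 0.0 | +22.1 |
| 50 | equal | 0.0 | +32.3 |
| 20 | lower on albiglutide | −19.0 | −7.3 |
| 35 | lower on albiglutide | −31.9 | −11.8 |
| 50 | lower on albiglutide | −45.0 | −16.4 |

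The formula agrees: for L = 50 and slope 1.145, 1.145 × 25 = 28.6, and −45.0 + 28.6 = −16.4. With equal doses, the incoming-dose model rejected in 5.9% to 6.5% of runs. The halved-dose model rejected in about 100%, in the wrong direction.

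**The case against.** The tempting stronger reading is that Baseline is the halved prescription, so the planned estimate and interval are simply wrong. The documents do not support that. The eCRF is not among them. SAP 11.3.4 says which visit label to use, not which dose on that record. Protocol 5.1.3.4 speaks of recommended rather than prescribed doses, so equating the two is an inference. Protocol 6.1 lists total daily insulin, including lispro, as a critical baseline assessment, and Protocol 8.3.3.2 gives the covariate's purpose as adjusting for chance differences. Both fit the incoming dose.

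A reader might also infer a route to a false claim of insulin reduction. The bias runs the other way. Nor would the test necessarily fail. Take a shrunken difference of −13.2 U and an assumed residual SD of 40 U with 337 per arm: the SE is 40 × √(2/337) = 3.1 and z is about −4.3, which still passes. All three simulated reductions also stayed significant in every run. A failed or reversed test needs a true reduction no larger than roughly the shift. That could follow from glargine titration or lispro re-introduction, but the documents do not show it.

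These points limit the claim to an undefined term with a conditional bias. They do not remove it: two readings of a confirmatory covariate differ by half the lispro dose in one arm, and the SAP does not choose between them.

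**Conclusion.** The concern holds as a gap in definition with a material consequence. The SAP does not identify the Baseline value for prescribed insulin dose, and its own visit rule and Week 25 logic lead most naturally to a value that randomisation has already changed in one arm. If that value is used, the adjusted Week 26 difference shifts against albiglutide by about b × L/2, or 5 to 25 U/day for assumed L of 20 to 50 U and b of 0.5 to 1.0. Every dose mean, SD and slope here is an assumption, so no fixed percentage of understatement can be stated.

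The effects would be an understated reduction, reduced power at that step of the hierarchy, and a false Baseline imbalance. Total and bolus dose analyses, in units and per kg, are exposed. Basal-only analyses are not, because the plan continues glargine unchanged at randomisation in both arms.

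**What to change.** In SAP 8.1.2.4 and 11.5.1, define Baseline for all prescribed-dose variables, in both arms, as the last prescription in force before randomisation, that is, at the end of the Standardization Period, taken from the Insulin Surveillance eCRF page. State that any prescription issued at Visit 4 after randomisation is post-baseline and is not used as BASE.

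The 3-day diary mean is not a suitable substitute. It would reverse the decision in SAP 2.1 and pair an actual-dose baseline with a prescribed-dose outcome.

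The cost is one definition and one derivation change, to be settled before the database is frozen. Prescriptions are already captured from Visit 2. No protocol amendment is needed and no dosing changes.

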
Supportive Secondary
 
 • To assess additional glycemic parameters, achievement of HbA_{1c} treatment goals, body weight, and total daily insulin dose 	
 • Additional glycemic parameters: 
 • HbA_{1c} change from Baseline over time • FPG change from Baseline at Week 26 and over time • Achievement of HbA_{1c} treatment goals: 
 • Proportion of subjects achieving a HbA_{1c} <7.0% at Week 26 and over time • Proportion of subjects achieving a HbA_{1c} <6.5% at Week 26 and over time • Incidence and time to meeting prespecified criteria for severe, persistent hyperglycemia at Week 26 • Additional assessments of daily insulin doses: 
 • Total daily insulin dose (24-hour total international units [IU] and total units/kg body weight) over the 3 days preceding the Baseline/Randomization and Week 4, 10, and 18 visits • Total daily basal insulin (insulin glargine) (24-hour total IU and total units/kg body weight) over the 3 days preceding the Baseline/Randomization and Week 4, 10, 18, and 26 visits • Total daily bolus insulin (insulin lispro) (24-hour total IU and total units/kg body weight) over the 3 days preceding the Baseline/Randomization and Week 4, 10, 18, and 26 visits • Total number of weekly insulin injections (7 days) to achieve glycemic control at Baseline/Randomization and Week 4, 10, 18, and 26 • Composite endpoints (after 26 weeks of treatment): 
 • Percentage of subjects achieving HbA_{1c} <7.0% without weight gain • Percentage of subjects achieving HbA_{1c} <7.0% without severe or documented symptomatic hypoglycemia • Percentage of subjects achieving HbA_{1c} <7.0% without weight gain and without severe or documented hypoglycemia

Objective	Endpoint

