2. Modified based on the insulin titration algorithms in the BEGIN basal-bolus type 2 study [Garber, 2012] and other published treat-to-target studies [Rosenstock, 2008; Abrahamson, 2012; Mathieu, 2014; Riddle, 2014].
3. Investigator may defer adjustment if there is an obvious reason for the low value such as a missed meal.

Any insulin titration that differs from the algorithm recommended dose must be commented on by the investigator and the reason documented on the appropriate page of the eCRF. If adequate documentation is not provided in the eCRF, a protocol deviation will be recorded.

If the before breakfast glucose target has been achieved, but it is felt that the basal insulin needs further optimization, then alternatives (e.g., moving the basal injection to the morning or splitting the basal dose into twice daily injections) can be discussed with the medical monitor overseeing the titration and documented.

Insulin Lispro Titration

Insulin titration should start with insulin glargine given before bedtime. After about 6 weeks, it is expected that the basal insulin glargine dose will have been stabilized and the insulin lispro titration may begin.

Following randomization to study medication, insulin lispro will be titrated differently in each treatment group.

In the albiglutide plus insulin glargine group, the insulin lispro dose will be downtitrated at the Baseline/Randomization visit to half that used at the end of the Standardization Period. At Week 4, insulin lispro will be completely discontinued and should remain discontinued for the remainder of the Treatment Period; unless the subject meets the criteria for insulin lispro re-introduction (see Section [5.1.3.5](#)).

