≤99 without obvious explanation	≤5.5 without obvious explanation	-2 ³ For a dose >50 U, consider a 5% to 10% dose reduction at the discretion of the investigator
100 – 119 = Target	5.6 – 6.6 = Target	No adjustment
120 – 139	6.7 – 7.7	+2
140 – 179	7.8 – 9.9	+3
≥180	≥10.0	+4
If severe hypoglycemia (requiring assistance) or any other clinically significant hypoglycemia was documented since the last dose adjustment		Decrease insulin dose at the investigator's discretion (i.e., 10% to 15%)

1. Mean of measurements from the last 3 available days (at least 2 of which are consecutive) in the week before the next study visit/telephone contact. If measurements from 3 days (at least 2 of which are consecutive) are not available, the dose adjustment should be delayed until the next scheduled study visit/telephone contact, unless in the investigator's judgment, a dose adjustment is warranted at that time. The subject should be retrained on the importance of self-monitored blood glucose measurements (SMBG).
2. Modified based on the insulin titration algorithms in the BEGIN basal-bolus type 2 study [Garber, 2012] and other published treat-to-target studies [Rosenstock, 2008; Abrahamson, 2012; Mathieu, 2014; Riddle, 2014].
3. For subjects with an SMBG value less than 70 mg/dL without obvious explanation, insulin lispro may be stopped at the investigator's discretion.

Any insulin titration that differs from the algorithm recommended dose must be commented on by the investigator and the reason must be documented on the appropriate page of the eCRF. If adequate documentation is not provided in the eCRF, a protocol deviation will be recorded.

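### SAP 8.1.2.4 counts weekly injections by different rules in the two arms, so comparator departures from the default regimen cannot show

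*SAP*

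**What the plan says.** Protocol Section 2 lists as a supportive secondary endpoint "Total number of weekly insulin injections (7 days) to achieve glycemic control at Baseline/Randomization and Week 4, 10, 18, and 26". Protocol 3.1 names the number of injections per week among the measures that the treat-to-target design is meant to make comparable. The rationale (Protocol 1.2) expects 28 a week on basal-bolus, with 21 given as the upper limit for bolus injections, against potentially 8 on albiglutide plus basal.

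SAP 8.1.2.4 states that "the value for this analysis is derived based on the number of prescribed insulin injections as follows" and then lists three set values: "Albiglutide: 1 injection per week"; "Insulin Glargine: 1 injection per day (7 injections per week"; "Insulin Lispro: 3 injections per day (21 injections per week". It makes one exception. For albiglutide subjects whose lispro is re-introduced, the lispro count comes from the Surveillance eCRF page and may be one, two or three a day. At Week 26 in the albiglutide arm the lispro count is the Week 25 value, and "For glargine number of injections at Week 26 will be considered 1 per day".

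Protocol 5.1.3.2 allows regimens that depart from these values. For glargine, "splitting the basal dose into twice daily injections) can be discussed with the medical monitor". For lispro, footnote 3 to Table 4 says that after a low glucose reading without obvious explanation "insulin lispro may be stopped at the investigator's discretion".

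The set values are not among the changes from the protocol listed in SAP 2.1.

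**The concern.** The endpoint is meant to show how many injections each strategy needed once insulin had been titrated. In the comparator, the derivation gives the same answer however titration went. A comparator subject whose lispro was stopped is still recorded at 21 lispro injections, and a subject in either arm on twice-daily glargine is still recorded at 7. In the albiglutide arm, by contrast, lispro after re-introduction is counted as prescribed. The same drug is thus counted in one arm and assumed in the other.

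Fewer injections is one of the benefits the protocol expects to demonstrate, so a reader of the study report will take the table as an observed comparison. There is also a modelling consequence. Protocol 8.3.3.2 plans an MMRM for this endpoint and SAP Table 4 marks a statistical analysis, whereas SAP 8.1.2.4 and Table 2.68 provide descriptive statistics only. A model fitted to an arm with zero variance would say little.

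**Working it through.** **Inputs (SAP 8.1.2.4).** Albiglutide 1, glargine 7 and lispro 21 injections a week; re-introduced lispro 7, 14 or 21 a week as recorded.

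**The protocol's own figures.** Comparator: 7 + 21 = 28. Albiglutide arm without lispro: 1 + 7 = 8. Difference: 28 − 8 = 20. These are the rationale's figures, obtained without using any trial data.

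**Week 5.** Lispro is stopped in the albiglutide arm at Week 4 and may be re-introduced only after Week 8 (Protocol 5.1.3.5). At Week 5 the rule therefore gives 28 against 8, a difference of 20, for any data.

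**Weeks 10, 18 and 26.** Let r be the share of albiglutide subjects on re-introduced lispro and k their mean lispro injections per day. An albiglutide subject on re-introduced lispro scores 15, 22 or 29 for one, two or three a day. The arm mean is 8 + 7rk, so the difference is 28 − (8 + 7rk) = 20 − 7rk. The documents do not give r, so a range is assumed:

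| r (assumed) | k = 1 | k = 2 | k = 3 |
|---|---|---|---|
| 0.10 | 19.3 | 18.6 | 17.9 |
| 0.25 | 18.25 | 16.5 | 14.75 |
| 0.50 | 16.5 | 13.0 | 9.5 |
| 1.00 | 13 | 6 | −1 |

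The later difference can run from 20 to −1, but only through the albiglutide arm; the 28 never moves.

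**What the set values miss.** Let s be the share of comparator subjects with lispro stopped, d the daily injections lost (1 if one mealtime dose, 3 if all; footnote 3 does not say which), and q_c and q_a the shares with split glargine in the comparator and albiglutide arms.

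- Counted comparator mean = 28 − 7ds + 7q_c
- Counted albiglutide mean = 8 + 7rk + 7q_a
- Recorded minus counted difference = 7ds + 7(q_a − q_c)

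All shares here are assumptions:

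- s = 5%, 10%, 20% with one dose stopped: comparator mean 27.65, 27.3, 26.6 instead of 28.
- s = 5%, 10%, 20% with all lispro stopped: 26.95, 25.9, 23.8.
- Glargine split in 5%, 10%, 20% of an arm: glargine mean 7.35, 7.7, 8.4 instead of 7.

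The first error term can only overstate the difference. The second can go either way and cancels if splitting is equally common in both arms. For example, s = 5% with d = 1, q_c = 20% and q_a = 0 gives 0.35 − 1.4 = −1.05, an understatement. With s = 20%, d = 3, q_a = 20% and q_c = 0 it gives 4.2 + 1.4 = +5.6.

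**Albiglutide in the total.** Insulin only, with no re-introduction, the contrast is 28 − 7 = 21. Counting albiglutide makes it 20.

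**The case against.** The strongest defence is that the set values are the default regimen. Protocol 5.1.1 moves everyone to once-daily bedtime glargine and lispro at three main meals, and Table 2 has the comparator continue those doses at the start of treatment. The departures are exceptions: splitting glargine arises only after the pre-breakfast target is met and goes through the medical monitor, and stopping lispro is tied to low readings. The endpoint is supportive, SAP Appendix 10 leaves it outside the test hierarchy, and SAP 8.1.2.4 asks only for descriptive statistics. Lower bolus use in the comparator would still appear in the prescribed lispro dose analyses (Tables 2.65 and 2.66) and the Insulin Surveillance listing (Listing 150). All of this stands, and it limits the weight of the point. It does not justify counting lispro in one arm and assuming it in the other.

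A reader might infer three stronger things that the documents do not support.

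- That the whole between-arm difference is set by assumption. It is at Week 5, but from Week 10 it depends on recorded re-introduction, which is the main unknown in the albiglutide arm.
- That counting the albiglutide injection inflates the benefit. It lowers it by 1 a week and agrees with the rationale's own count of 8. It is a labelling mismatch in an endpoint named for insulin.
- That the miscounts mostly favour albiglutide. Both arms follow the same glargine algorithm, and nothing in the documents gives the share of split glargine in either arm or of stopped lispro.

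**Conclusion.** The point holds in a limited form. The comparator value of 28 with SD 0 and the Week 5 difference of 20 follow from the rule alone. They rest only on reading the SAP's set values literally, a reading that the Week 26 glargine instruction supports. The later difference is part data, part assumption. The error from stopped lispro and split glargine cannot be sized from the documents; under the assumed shares of up to 20% it lies between about −1 and +6 injections a week, and its net direction is unknown. Severity is minor to moderate: the derivation of a listed endpoint cannot register events that the protocol permits, but no confirmatory conclusion depends on it.

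**What to change.** In SAP 8.1.2.4:

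- Replace the set lispro value with the number of non-zero prescribed lispro injections on the Insulin Surveillance eCRF page, in both arms and at every visit.
- Do the same for glargine if that page records its frequency. SAP 6.8 says only that it captures prescribed dose, so this must be confirmed. If frequency is not recorded, keep one a day, state it as an assumption, and correct documented split-dose cases.
- Keep the Week 25 lispro value for Week 26 in the albiglutide arm, but drop the fixed one-a-day glargine value there wherever frequency is recorded.
- In Table 2.68, report insulin-only and all-injection totals as separate rows.
- State whether the protocol's MMRM for this endpoint has been dropped and, if so, list that in SAP 2.1.

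The cost is SAP wording, programming and a check of the eCRF page, which the SAP already uses for lispro counts in the albiglutide arm. The downside is some missing counts and possibly a smaller reported difference.
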